Hospitals will send the results of 30 hand hygiene observations from each included intervention ward every four months in accordance with the plan for the implementation of NOST in hospitals. The first submitted results will constitute the baseline measurement.

When NOST has been performed for a year, new measurements will be taken in the intervention wards and corresponding baseline measurements in the control wards. This will also include a minimum of 30 hand hygiene observations from each ward. The measurements in both arms will be conducted by observers who have received training and gained experience with NOST measurements during the year NOST has been carried out in the intervention wards.

The measurements from intervention wards that have had NOST for one year will be compared with contemporaneous baseline measurements in the control wards. The difference in compliance with hand hygiene in the intervention arm compared to the control arm will constitute the effect of having implemented NOST and performed quality improvement measures for one year. Repeated measurements over time in the intervention wards will be used to investigate whether the effect has increased and remains throughout the study period, or if the effect diminishes before comparison is made after one year.

The primary outcome is the number of measured indications for hand hygiene and the number of hand hygiene performed on indicated events, the proportion of correct compliance, and variation in correct compliance in the form of intra-class correlation coefficient (ICC).

Comparison of HAIs in the two arms will be made using surveillance data that is routinely collected from all hospitals. This includes:

- infectious disease outbreaks reported to the Norwegian Institute of Public Health's webbased outbreak notification system (VESUV), including the microbiological cause of the outbreak and the number of people infected among patients and staff
- number of patients recorded with infections in cross-sectional studies conducted in the Norwegian Surveillance System for Antibiotic Use and Healthcare-Associated Infections (NOIS)
- number of patients receiving antibiotic treatment recorded in NOIS
- number of patients recorded with postoperative infections in the surveillance of infections in surgical sites (NOIS-POSI)

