The number of outbreaks per arm will be collected from VESUV. At the start of the evaluation period, we will ask participating hospitals to submit the number of full-time positions per included ward. The number of inpatients per ward per day will be obtained from NPR. The number of positions and inpatients will be used as denominators when estimating the secondary attack rate in outbreaks. The number of patients registered in NOIS will be compared to the number of daily inpatients registered in NPR. If the number of inpatients per day changes over time, we will make a new collection of the number of full-time positions to capture significant changes in the organization and size of included wards.

NOIS and NOIS-POSI are surveillance systems where numerators and denominators are registered. From these systems, it is sufficient to receive the results for each ward in the form of the proportion of patients with different types of infections.

From NPR, we will apply for data for all hospitalized patients at both intervention and control wards from and including 1. January 2020 up to the time of application in 2024, giving numerators and denominators for the periods before, during and after the intervention.

When comparing intervention and control groups, we will estimate relative risk (RR) and absolute risk difference (ARF) with 95% confidence intervals (table 2). We will report two-sided p-values where applicable and use the significance criterion p<0.05.

We will use modified Poisson regression to compare hand hygiene compliance one year after NOST was introduced in the intervention wards³. We will adjust for the factor used in stratification (hospitals) as a fixed effect.

Compliance will be analyzed and reported for each occupational group and total for all healthcare personnel. Outbreaks will be analyzed and reported as the number of outbreaks and secondary attack rate per arm, in total and distributed by patients and staff. The incidence of infection in patients will be analyzed and reported in total and by types of infection.

A more detailed description of the analyzes of the main and secondary outcomes will be published in a separate analysis plan.

[figure not shown]

Figure 1. Overview and schedule for the intervention and measurements in the evaluation

Table 2. Dummy table with results for compliance with hand hygiene recommendations

	Intervention arm	Control arm	ICC	Adjusted RR (95% CI)	ARF (95% KI)	p-value
Primary outcome						

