Compliance hand hygiene	540/900 ¹ (0.60)	369/900¹ (0.41)	0.020	1.683 (1.654 – 1.713)	0.279 (0.270-0.288)	<0.05

¹Number of hand hygiene performed by indicated events

Sample size

Sample size calculation (number of wards needed in each arm) is based on the following:

- Type I error rate: 0.05
- Power: 0.80
- Primary outcome is dichotomous with expected baseline proportion: 0.40
- Outcome is measured as simple difference at the end of the intervention period
- Intraclass correlation coefficient (ICC) of primary outcome: 0.10
- Expected number of measured events per cluster (hospital ward): 30
- Degrees of freedom used when adjusting for cluster-level covariates in the analysis: 2
- A priori stratification in the design and analyses
- Hypothesized intervention effect (increased proportion of compliance): 0.20

The estimation of necessary number of wards in both arms is conducted in parallel cluster-randomized trials calculator published by the National Institutes of Health (https://researchmethodsresources.nih.gov/grt-calculator).

Table 3 shows the function of the number of clusters (wards) per arm, and the number of events measured in each ward. The first row shows the number of clusters, while the first column shows the number of events measured per ward. The inner cells show the magnitude of the difference (increase in proportion) that we can identify as significant with a power of 80%. We assume that we

can detect a difference of at least 20%, and the calculations show that we have enough power for this if we have 26 wards in each arm, if there are 30 hand hygiene sessions measured in each ward.

Table 3. Detectable difference in the arms, distributed by number of participating wards per arm and number of events measured per ward

Absolute Detectable Difference Clusters (wards) per arm

		24	25	26	27	28
Events measured per ward	15	0,2266	0,2219	0,2175	0,2134	0,2094
	23	0,2113	0,2069	0,2028	0,199	0,1953
	30	0,2042	0,2	0,1961	0,1923	0,1888
	38	0,1992	0,1951	0,1912	0,1876	0,1841
	45	0,1962	0,1922	0,1884	0,1848	0,1814

Group allocation

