wards randomized and not excluded (see exclusion criteria, above). In practical terms, the data set
will have one ward per row and there will be 9 outcome variables (columns), plus covariates.
Outcomes will be analyzed in the arms to which the wards were randomized.

182 **7.3 Covariates and Subgroups**

183 Because randomization is stratified by hospital, we originally planned to adjust for hospital as a fixed 184 effect in all analyses. However, the planned adjustment would require estimating one parameter for 185 each hospital (minus the reference hospital), in addition to treatment effect. The large number of parameters that would therefore need to be estimated could lead to imprecision on the effect 186 187 estimates and possibly also estimation problems. Further, the trial is unlikely to include all hospitals 188 in Norway and hence the sample will not exhaust all possible levels of the hospital variable. For these 189 reasons, and the chosen regression model (see section 9), we will account for the likely clustering of 190 outcomes within hospital using cluster-robust standard errors, with hospital as the cluster variable.

191

192 We will obtain data on the following variables to support four subgroup analyses:

- 193
- 194 1. Hospital department (e.g., psychiatry, orthopedics, neurology, ...)
- 195 2. Employee profession (e.g., physician, nurse, ...)
- 196 3. Indications of hand hygiene (e.g., before patient contact, after exposure to body fluid,)
- 197

198 These subgroups are based on the hypothesis that baseline hand hygiene compliance may differ by 199 type of ward or type of profession with different levels of education or work tasks, and compliance 200 may vary depending on the situations in which hand hygiene is recommended. It may be the case that 201 treatment effect is different in these subgroups. (For example, if some ward types already have 202 exceptionally high baseline compliance with hand hygiene recommendations, then only a small 203 beneficial treatment effect is possible for this subgroup. Conversely, if a type of ward or profession 204 has exceptionally low baseline compliance for all or some of the indications then a large beneficial 205 treatment effect may be achievable in this subgroup.

206

207 7.4 Multiple Centers

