With respect to the primary outcome, n_i is the number of compliances in the *i*th hospital ward, N_i is the number of observations made in the *i*th hospital ward, β_0 estimates log risk in control, x_i indicates if the *i*th hospital ward was randomized to NOST, β_X estimates the effect of being randomized to NOST as a marginal log risk ratio. The marginal log risk ratio of being randomized to and adhering to NOST is estimated by β_X .

If 5% or more wards do fully not adhere to their randomized treatment, we will estimate marginal risk
 ratios (RRs) using binomial regression as follows:

354 355 356

 $n_i \sim B(N_i, p_i)$ where $\log p_i = \beta_0 + \beta_X x_i + \beta_A a_i$

357 Here, $0 \le a_i \le 1$ models the degree of adherence by the *i*th hospital ward to NOST (see section 7.6) 358 with $\alpha_i = 0$ corresponding to non-adherence and $\alpha_i = 1$ corresponding to full adherence, and β_A 359 estimates the effect of full adherence to NOST. The marginal log risk ratio of being randomized to and adhering to NOST is estimated by $\beta_X + \beta_A$. Note that the x_i and a_i may be highly correlated (almost 360 collinear) because we expect that most wards that implement NOST will also adhere to NOST. For this 361 reason, we will not interpret β_X and β_A separately. We will assume that the statistical software will 362 cope well with the high correlation but will address this issue during analysis in the case of 363 364 nonconvergence.

365

366 Estimation can be performed using Stata as follows (see footnote 1 on page 14):

367 368 binreg compliances i.treat c.adh, n(observations) rr vce(cluster hospital) 369

370 where data are arranged with one ward per row, compliances is a variable containing the numbers

of observations where the employees comply, treat is a treatment indicator where 1 indicates randomization to NOST, adh is a variable containing adherences (which would be omitted if fewer than 5% of wards do not adhere to their randomized treatment), observations is a variable containing the numbers of observations made, and hospital is a factor variable that codes for the hospital to which the wards belong. Treatment effect can then be estimated on the log scale using:

lincom _b[1.treat] + _b[adh]

379 Estimation can be performed using R as follows:

If the analysis is performed in R after imputation (see section 7.5), the script will be run in a loop

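### SAP 7.3 takes the stratification factor, hospital, out of the outcome models for a precision reason that does not hold, and gives the hospital-clustered test that replaces it no small-sample reference

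*SAP*

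**What the plan says.** The protocol (Group allocation) randomises wards within hospital, aiming for equal numbers per arm in each. For the primary comparison it names modified Poisson regression and adds: "We will adjust for the factor used in stratification (hospitals) as a fixed effect". SAP section 6 also lists stratification by hospital among the sample-size assumptions.

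SAP 7.3 withdraws the adjustment for all analyses. It gives three reasons: one parameter per hospital could make the effect estimate imprecise or cause estimation problems, the hospitals are only a sample of those in Norway, and the choice of regression model. Instead it will account for clustering of "outcomes within hospital using cluster-robust standard errors, with hospital as the cluster variable". The models in 9.1 and 9.2 accordingly contain only treatment and, if needed, adherence. The Stata call for count outcomes is "binreg compliances i.treat c.adh, n(observations) rr vce(cluster hospital").

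The SAP names no reference distribution, degrees of freedom, small-sample correction or minimum number of hospitals. Hospital does remain in the imputation model (SAP 7.5).

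**The concern.** Two things are at stake.

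- **Precision.** Leaving out a stratification factor usually costs precision, or at best nothing. Here it is left out in order to protect precision. Counts per ward need not be equal, since the protocol says: "This will also include a minimum of 30 hand hygiene observations from each ward". SAP 4.1 promises only approximately equal allocation within hospital, and some wards may not report. Each of these lets differences between hospitals enter the unadjusted risk ratio.
- **Type I error.** A sandwich variance clustered on hospital is estimated from as many independent pieces as there are hospitals. Compared with 1.96, it rejects too often when hospitals are few. Participation is voluntary, hospitals can be excluded after randomisation, and the sample size is fixed in wards only. For infections within outbreaks (SAP 10.2.2 and 10.2.3) only wards with a reported outbreak are analysed, so fewer hospitals may contribute.

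**Working it through.** **Inputs from the documents.** "Type I error rate: 0.05"; "We will report two-sided p-values where applicable and use the significance criterion p<0.05"; "Primary outcome is dichotomous with expected baseline proportion: 0.40"; "Hypothesized intervention effect (increased proportion of compliance): 0.20"; ICC 0.10; 30 events per ward; 26 wards per arm; three to five reporting wards per hospital; around 60 hospitals expected.

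**Assumed.** The share of the ICC lying between hospitals (0 to 0.7), the number of hospitals at 52 wards, and the spread of counts per ward.

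**1. The plan's own figure.** Protocol Table 3 is reproduced by (t₀.₉₇₅ + t₀.₈₀) × √{2 × 2p(1−p)[1+(m−1)ICC]/(mg)} with df = 4(g−1)−2. For g = 26 and m = 30, df = 98 and (1.984 + 0.845) × √{2 × 0.48 × 3.9/780} = 0.1961, as printed. All 25 cells match. The leading factor 2 is my inference from the match. The number of hospitals does not enter.

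**2. Hospitals implied by 52 wards.** Three to five reporting wards plus as many controls is 6 to 10 wards per hospital. 52/10 = 5.2 and 52/6 = 8.7, so about 6 to 9 hospitals.

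**3. Type I error of the SAP test.** The unadjusted log RR is log(p₁/p₀), with each pᵢ pooled over the wards in an arm. Its variance is G/(G−1) × Σ over hospitals of (sum of ward influence terms)². A log-binomial fit gave the same estimate and standard error. Simulation under RR = 1 used control risk 0.40, total ICC 0.10 and 30 or more events per ward. There were 40,000 runs per setting at 52 wards and 6,000 at 60 hospitals (360 or 600 wards).

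| Hospitals G | Against 1.96 | Against t(G−1) | Theory: t(G−1) tail beyond 1.96 |
|---|---|---|---|
| 6 | 10.0–11.8% | 4.5–5.8% | 10.7% |
| 7 | 9.5–9.8% | 4.8–5.1% | 9.8% |
| 8 | 8.7–9.4% | 4.7–5.2% | 9.1% |
| 9 | 8.4–8.7% | 4.8–5.1% | 8.6% |
| 13 | 7.1–7.3% | 4.7–4.9% | 7.4% |
| 60 | 4.8–5.4% | 4.4–5.0% | 5.5% |

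Poisson with hospital fixed effects, a ward-level sandwich and t gave 4.4–5.4% in layouts of 48–60 wards.

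**4. Precision.** Conditional Poisson solves Σ over hospitals of {y₁ − Y·θN₁/(θN₁+N₀)} = 0. Here y₁ is the intervention-arm compliances in a hospital, Y the compliances in both arms, and N₁ and N₀ the observations in each arm. If N₁/N₀ = r in every hospital, the fraction is the constant θr/(1+θr), and the solution is the pooled, unadjusted risk ratio. So conditioning neither costs nor gains anything in that case. Simulation agrees: with 7 hospitals of 8 wards the empirical SD is 0.0941 either way.

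Otherwise the variance reduction depends on imbalance (hospital share of the ICC 0.3–0.7; layouts 7×8, 9×6 and 60×8):

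| Setting | Variance reduction |
|---|---|
| 30 per ward, balanced arms | 0% |
| 30 plus 0–19 per ward, balanced arms | 1–3% |
| 30 per ward, 10% of wards missing | 1–10% |
| 30 plus 0–19 per ward, 10% missing | 1–12% |
| 30 plus a geometric extra (mean 60), balanced arms | 9–24% |

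With odd ward numbers (8×7 and 10×5) and modestly variable counts, the variance ratios were 1.046–1.111 at hospital shares of 0.3–0.5, a reduction of about 4–10%. At a share of 0.7 they were 1.214 and 1.264, or 18% and 21%. Conditioning did not lose precision in any setting.

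**The case against.** The case for the SAP is substantial.

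- **Expected size.** The protocol expects around 60 hospitals and several hundred wards, and 52 wards is a floor. At 60 hospitals the test is close to nominal. This stands: a reader might infer that the trial as planned has about 9% type I error, and the documents do not support that.
- **Precision.** Allocation is balanced by design, SAP section 6 gives 30 as the average count, and the hospital-clustered variance already removes between-hospital variation (mean SE 0.0905 against an empirical SD of 0.0941 in the 7×8 layout). Multiple imputation covers part of any missingness. This stands too: a reader might infer a large loss of precision, but that needs strongly skewed counts or marked imbalance, which the documents do not describe.
- **Normal quantiles.** These are the `binreg` default and are not stated in the SAP. Stata `regress` with clustering uses t(G−1), so the error-rate point does not reach bed-days in Stata. The R code for 9.1 was not legible in the copy available to me. The R code in 9.2 names no degrees of freedom.
- **Hospital is not discarded.** It defines the variance clusters and stays in the imputation model.
- **Estimation problems.** SAP 7.3 is open about the change, and many hospital terms can trouble a log-binomial fit. That argues against the log-binomial model. It does not argue against the protocol's Poisson model, where hospital effects can be conditioned out.
- **Scope of inference.** Ward-level standard errors conditional on hospital suit a common risk ratio. If the effect varies between hospitals, hospital-clustered inference answers the broader question. The simulations did not vary the effect, so this remains a fair reservation about the choice of standard error.

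**Conclusion.** The concern holds in a limited form. The SAP departs from the protocol by leaving the stratification factor out of all outcome models, and its imprecision argument fails for a Poisson model.

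The gain from restoring hospital is nil with equal counts and equal allocation, and about 1–10% of variance with modest count variation, missing wards or odd ward numbers. It reaches about 12–22% or more only with highly variable counts, or similarly if most of the ICC lies between hospitals and ward numbers are odd. The count spread and the ICC split are assumptions.

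For count outcomes, normal quantiles without a small-sample correction give about 8–12% type I error in 6–9 hospitals at 52 wards, about 7% at 13 hospitals, and about 5–6% at 60. The range of 6–9 hospitals is inferred from the ward minimum. The error-rate point is therefore a safeguard against low participation and sparse outcome sets. It is not a defect at the expected size.

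**What to change.** Before unblinding, amend SAP 7.3, 9.1 and 9.2:

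1. Keep hospital as a stratum, as the protocol planned. Use modified or conditional Poisson for the primary outcome and for other count outcomes where events allow, and hospital fixed effects for bed-days.
2. Use robust standard errors with a t reference. State whether they are taken at ward level (df = wards − hospitals − 1; for example 52 − 9 − 1 = 42) or at hospital level with t(G−1), and why.
3. If the hospital-clustered sandwich without hospital in the model is kept, pre-specify t(G−1) or CR2 in place of normal quantiles, and write it into both the Stata and the R code.
4. State how many hospitals the chosen reference needs.

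The cost is wording and code, plus a few degrees of freedom. Hospitals with wards in only one arm, or with no events, contribute nothing to the conditional estimate, which matters most for outbreaks. Under option 3 the critical value rises from 1.96 to 2.57 with 6 hospitals or 2.31 with 9, so intervals are about 31% or 18% wider (2.57/1.96 and 2.31/1.96). At 60 hospitals it is 2.00 and the change is negligible.

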We will not combine outcomes by ward or hospital (i.e., we will not define "pseudo-centers"). We will not explore treatment-by-hospital interactions. Between-hospital differences in risk of compliance, for example, will be accounted for using cluster-robust standard errors with hospital as the cluster variable.

212 **7.5 Missing Data**

We will examine the data for spurious values and seek to verify or obtain correct values if data are miscoded (e.g., negative counts, nonintegral values entered for counts, or counts that appear to be unrealistically large). We will report any data processing decisions that need to be made at the time of analysis.

217

218 It is very unlikely that data will be missing for the treatment, hospital, or ward variables, which are219 needed in all analyses.

- 220
- 221 Data may be missing for the primary outcome variable, which is measured by observers. It is unlikely

- that data will be missing for the secondary outcome variables, which will be obtained from registries,
 but data will be missing if hospitals do not provide data to the registries (Norwegian Institute of Public
- 224 Health).
- 225

If wards do not provide outcome data for the primary outcome, we will contact them and ask them to provide the missing data. If more than 5% of wards do not provide primary outcome data, we will use Little's test to assess if the data are unlikely to be missing completely at random (MCAR) but missing at random (MAR). If we assess the data to be MAR, we will use multiple imputation by chained equations (MICE) and perform the prespecified analyses including all wards.

231

The primary outcome comprises counts of observations and counts of those observations that meet the criteria for compliance. We anticipate that both counts will be missing for wards that do not provide outcome data. It will therefore be necessary to impute missing values for these variables in a way that ensures both are valid counts, and that the number of compliances is not greater than the number of observations imputed for a given ward. We will do this as follows.

237

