238 For each ward with non-missing primary outcome data, we will compute a point estimate of the 239 logit risk of compliance as $w_i = \log r_i - \log(1 - r_i)$, where $r_i = n_i/N_i$. Within the MICE 240 framework, we will impute logit risks for wards with missing primary outcome data (e.g., using a linear 241 model with normal errors), and hence risks for wards with missing primary outcome data as $r_i = 1/(1 + e^{-w_i})$, where w_i is an imputed logit risk. Missing observation counts (N_i) will be modelled 242 using a Poisson model. This may impute that no observations were made in some wards. We will 243 244 address this issue by replacing zero observation counts with ones. Finally, we will impute the number of compliances for the wards with missing primary outcome data as the passive variable $|N_i r_i + 1/2|$ 245 246 (i.e., "rounding half up" a possibly non-integral number of imputed compliances to an integer), where 247 N_i and r_i are imputed as described above. The r_i will not be used in subsequent analyses.

- 248
- 249 The imputation model for the primary outcome will include:
- 250251 Treatment assignment
- Adherence (if available; see section 7.6)
- Hospital (assuming data are not missing for all wards in a hospital)
- Hospital region
 - Type of department
 - The secondary outcomes (on the basis that the primary outcome is likely to be highly correlated with other outcomes)
- 257 258

255

256

259 If we cannot assess that the data are likely MAR and cannot rule out the possibility that the data are 260 missing not at random (MNAR), we will perform complete case analyses, but will not draw strong 261 conclusions about the causal effect of NOST and report the missing data as a possible limitation.

262

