263 The secondary outcomes depend on registry data. It is possible that some wards or hospitals will either 264 never report data or will intermittently report data. Both possibilities represent missing outcome data 265 problems. We will therefore follow the same general approach as for missing primary outcome data. 266 In the case that secondary outcome data is known to be intermittently reported (i.e., data for some collection periods are available for certain wards, but no data have been reported by the wards for 267 268 other periods), we will use MICE to impute for the collection periods with missing data and then 269 compute the total number of inpatients infected (for example). The imputed outcome is therefore a function of imputed variables (a "passive" variable), which should be handled carefully in the analysis. 270 271 In Stata, it is necessary to use the syntax "mi passive: generate..." or 272 "mi register passive...", prior to "mi estimate:..." to ensure the passive variables are generated correctly in the imputed data sets. In R, passive variables can be handled using the approach
described in section 3.4 of van Buuren and Groothuis-Oudshoorn [1].

275

276 Unless legally or ethically prohibited, we will report any missing data and wards or hospitals that 277 cannot be included in analysis, for example due to withdrawal from the trial.

278 7.6 Intercurrent Events

279 Recall from section 3.2 that the research question is about the effect of implementing and adhering 280 to NOST. We anticipate that some wards may not adhere or fully adhere to the treatment to which 281 they were randomized. For example, a ward may have been randomized to implement and adhere to 282 NOST for the one-year period of the trial, but either did not implement NOST or did not fully adhere. 283 Similarly, a ward may have been randomized to the control arm (i.e., to not implement NOST), but 284 NOST was partially or fully implemented. Because such events would occur after randomization and 285 would change the interpretation of the outcome from that originally intended and hence give a 286 treatment effect estimate that does not have the intended interpretation, non-adherence can be 287 treated as an intercurrent event (ICE) [2].

288

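### SAP 7.5: the imputation logit is infinite for wards at 0% or 100% compliance, and Little's test cannot establish MAR, yet it is the only stated basis for choosing between imputation and complete cases

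*SAP*

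**What the plan says.** All of this is in SAP 7.5 (Missing Data) unless another section is named.

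- **Trigger.** The rules start at "If more than 5% of wards do not provide primary outcome data".
- **Test.** The team then uses Little's "test to assess if the data are unlikely to be missing completely at random (MCAR) but missing at random (MAR"). If the data are assessed to be MAR, MICE is used and all wards are analysed.
- **Imputation scale.** "For each ward with non-missing primary outcome data, we will compute a point estimate of the" logit risk, defined as log r − log(1 − r) with r = n/N. This is imputed, for example with a linear "model with normal errors), and hence risks for wards with missing primary outcome data as" the inverse logit of the imputed value.
- **Boundary repair.** An imputed number of observations can be zero, and the SAP will "address this issue by replacing zero observation counts with ones". It gives no rule for an observed ward with n = 0 or n = N.
- **Fallback.** "If we cannot assess that the data are likely MAR and cannot rule out the possibility that the data are" MNAR, complete cases are analysed, strong causal conclusions are withheld and the missing data are reported as a limitation.
- **Secondary outcomes.** "We will therefore follow the same general approach as for missing primary outcome data". For intermittent reporting, the missing collection periods are imputed and then summed.

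**The concern.** There are two separate faults in one section.

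First, the transformation is not defined for every ward to which it must be applied. One infinite value makes a least-squares fit return no estimate. The analyst must then drop the ward or choose a correction at the time of analysis. Dropping removes the wards with the most extreme compliance from the model that generates the imputations.

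Second, the choice between two analyses of the primary outcome rests on a test that does not address the question. Little's test asks whether the data are MCAR. It cannot separate MAR from MNAR, and that distinction is what the plan uses to choose between imputation and complete cases. With no other criterion written down, the choice falls to judgement at analysis. One of the two routes, complete cases, gives no protection against informative missingness.

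Missing wards are plausible: the Protocol makes participation voluntary, including the control-ward measurement, and SAP 7.5 accepts that primary outcome data may be missing.

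**Working it through.** **Inputs.** From the Protocol (Sample size) and SAP 6: N = 30 observations per ward, ICC 0.10, compliance 0.40 and 0.60, 52 wards. From the Protocol (Group allocation): about 60 hospitals with up to 10 wards each, so at most 60 × 10 = 600 wards. The Protocol's dummy Table 2 shows an ICC of 0.020, used here as a low value. Assumptions: ICC 0.20, compliance 0.80 and 0.90, and 200 wards as an intermediate number. The plan gives no figure of its own for how often a ward is at a boundary, so there is none to reproduce. The 52 wards are taken as stated.

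**1. The logit at the boundary.** For n = 0: log(0) − log(1) = −∞. For n = N: log(1) − log(0) = +∞. With a 0.5 correction, log((n + 0.5)/(N − n + 0.5)) gives log(0.5/30.5) = −4.11 for 0/30 and log(30.5/0.5) = +4.11 for 30/30.

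**2. How often it happens.** Let ward compliance follow a beta distribution with a = μs, b = (1 − μ)s and s = 1/ICC − 1, so s = 9 at ICC 0.10. With B the beta function, the share of wards at a boundary is

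q = B(a, b + 30)/B(a, b) + B(a + 30, b)/B(a, b).

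At μ = 0.40 (a = 3.6, b = 5.4), q = 0.00211 + 0.00004 = 0.00215. At μ = 0.60 the two terms swap and q is the same. The chance of at least one such ward in W wards is 1 − (1 − q)^W.

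| ICC | Compliance | q | W = 52 | W = 200 | W = 600 |
|---|---|---|---|---|---|
| 0.10 | 0.40 or 0.60 | 0.2% | 11% | 35% | 73% |
| 0.02 | 0.40 or 0.60 | 0.001% | <1% | <1% | <1% |
| 0.20 | 0.40 or 0.60 | 2.0% | 65% | 98% | >99% |
| 0.10 | 0.80 | 5.6% | 95% | >99% | >99% |
| 0.10 | 0.90 | 25% | >99% | >99% | >99% |

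**3. What dropping those wards does.** In 400,000 simulated wards (N = 30, ICC 0.10), normal logits were drawn with the observed mean and SD and back-transformed. No covariates were used.

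| True compliance | Mean imputed risk, boundary wards dropped | Mean imputed risk, 0.5 correction |
|---|---|---|
| 0.40 | 0.399 | 0.402 |
| 0.60 | 0.600 | 0.598 |
| 0.80 | 0.789 | 0.790 |
| 0.90 | 0.869 | 0.888 |

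**4. Secondary outcomes, if the same logit were used.** SAP 5.2 gives outbreaks the denominator of wards, and SAP 7.2 puts one ward in each row. Each row then has N = 1. A 0/1 count gives r = 0 or r = 1, and the logit is infinite in every ward.

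**5. What Little's test can show.** Its null is MCAR.

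- Rejection: MCAR is doubtful. MAR and MNAR both remain.
- Non-rejection: MCAR is not established, and SAP 7.5 names no branch for this result. Just above the trigger in 52 wards (0.05 × 52 = 2.6), the test compares 3 wards with 49. In 600 wards (0.05 × 600 = 30) it compares 31 with 569.

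An illustrative simulation assumed 200 wards, about 15–20% of them missing, and a true difference of 0.20:

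| Mechanism | Little's test rejects | Bias, complete cases | Bias, imputation |
|---|---|---|---|
| MCAR | 5% | 0.000 | 0.000 |
| MAR | 63% | +0.008 | 0.000 |
| MNAR, first form | 24% | +0.017 | +0.013 |
| MNAR, second form | 9% | +0.015 | +0.015 |

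The test rejected less often under either MNAR form than under MAR. Complete cases were never less biased than imputation. The sizes depend on the assumed mechanisms.

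**The case against.** Much can be said for the plan. The rules apply only above 5% missing wards. The linear model is offered as an example. An infinite value is conspicuous when code runs, SAP 12 requires testing on fictitious data, and SAP 7.5 promises to report data-processing decisions. At the planning values the imputed risks hardly change. In the complete-case branch the SAP holds back from strong conclusions. These points limit the harm. They leave the raw logit prescribed with no boundary rule, and a caveat does not replace a sensitivity analysis. The sensitivity analyses in SAP 9.1.1 and 9.2.1 concern adherence, not missing data.

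A reader might infer three stronger things that the documents do not support.

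- **That complete cases are always available because MNAR can never be excluded.** The fallback has two conditions: MAR cannot be assessed as likely, and MNAR cannot be ruled out. A team that judges MAR likely goes to imputation. The gap is that no criterion for that judgement is given beyond Little's test.
- **That imputation of infection outcomes fails, or is biased upwards, as written.** The logit is written for compliance only. For secondary outcomes the SAP promises the same general approach, without naming the logit or a normal model, and it expects missing registry data to be unlikely. The documents give no ward-level infection rates, and these outcomes are totals over one year, so it cannot be said that zero is the usual value. Step 4 is therefore conditional.
- **That Little's test carries no information.** It is informative about MCAR. It is uninformative about MAR against MNAR.

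**Conclusion.** Both faults stand, within limits. The logit in SAP 7.5 is undefined at 0% and 100% compliance, and the only boundary repair concerns an imputed count of zero observations. Under a beta-binomial model with the plan's N = 30 and ICC of 0.10, this is a small risk in 52 wards and a likely event in 600. The bias is negligible at compliance 0.40 to 0.60. It becomes visible only at high compliance (0.869 against 0.888 at an assumed 0.90, for imputed wards only), which matters because SAP 7.3 itself considers ward types with very high baseline compliance. The main cost at the planning values is a failed model or an unplanned repair.

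The test-based switch is a fault of logic and does not depend on those figures. Little's test cannot support a finding of MAR, non-rejection has no stated consequence, complete cases are no remedy for MNAR, and no MNAR sensitivity analysis is planned. The section should be corrected before analysis. Neither fault has any effect if 5% or fewer of the wards lack the primary outcome.

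**What to change.** - **Imputation scale.** Replace the raw logit by log((n + 0.5)/(N − n + 0.5)), or impute compliance counts directly from a binomial or beta-binomial model.
- **Secondary outcomes.** Name the imputation model for each one. Count models (Poisson or negative binomial, or binomial with the stated denominator) avoid the boundary problem.
- **Choice of analysis.** Do not let Little's test decide. Above 5% missing wards, make multiple imputation under MAR the main analysis, justified by what is known about why wards fail to report, and complete cases a sensitivity analysis.
- **MNAR.** Add a delta-adjusted analysis that shifts the imputed logits over a range the team justifies in advance, and report the shift at which the conclusion changes.

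The cost is a revised SAP 7.5 and a few lines of code. No new data are needed.
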